**Protocol ID: ADA-1**

**04/01/19**

## Study design

The null hypothesis of this comparative randomized clinical trial is that the intervention with either type of anesthesia is equally perceived by the patient.

Forty-eight patients needing implant placement in the posterior mandible, were enrolled in this prospective study, by eight different surgeons in eight different private dental centers with similar settings and socio-professional characteristics, following the same operating protocol, which had previously been thoroughly discussed among the participants.

All the patients were randomly included in one of the two groups: A (for interventions with IANB) and B (for interventions with INF) and assigned in equal proportions to surgeons. The "List Randomizer" (<https://www.random.org/lists>) was used as randomization method. When a participant surgeon had a patient to place implants in the posterior mandible, phoned to a person not participating in the study, to obtain the method of anesthesia to be used in this particular patient thirty minutes before intervention started.

The procedures were fully explained to the patients and all signed an informed consent for their voluntary participation in the study. The study was approved by the Ethic Committee of San Juan Hospital of the University Miguel Hernandez, Alicante, Spain.

The primary outcomes were pain perception by the patient during surgical procedure and patient's satisfaction 12 hours after operation. Data from patient's perceptions were collected using a Numerical Rating Scale (NRS) four times, three for pain perception (after incision, after drilling, after suturing) and one for global satisfaction (12 hours after operation).

Five confounding variables were also recorded: gender, the use of release incision, the number of implants placed, whether or not bone regeneration (GBR) was applied and the distance from the implant apex to the mandibular canal.

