## Statistical analysis

According to a previous calculation of the sample size, a minimum of 48 patients (24 per group) were determined to be necessary to reach a power of 75% with a Mann-Whitney test, a confidence level of 95% and a magnitude of 0.8 (strong) in pain level to be detected.

Data were tabulated to calculate descriptive statistics for all the variables of the investigation. Descriptive tables for the two primary variables were also tested by the five confounding variables. First, the homogeneity of two groups was verified. For the bivariate analysis, non-parametric tests were used:

- the chi-square and Fisher's exact tests were used as for groups homogeneity,
- the Mann-Whitney test to analyze the influence of the group on pain or satisfaction,
- the Spearman coefficient to measure the correlation between the two primary outcomes
- Friedman's test to check if the pain level was similar in incision, drilling and suturing.

For all tests, the significance level was set at 5% ( $p < .05$ ).

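### Does calling four features of the operation confounders, when the surgeon already knows the anesthesia, undermine the analysis?

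*Combined protocol and SAP*

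**What the plan says.** In the Study design section, the surgeon with an eligible patient phones someone outside the study "to obtain the method of anesthesia to be used in this particular patient thirty minutes before intervention started". The eight surgeons work "following the same operating protocol, which had previously been thoroughly discussed among the participants"; the document does not reproduce the rules of that protocol.

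The same section names five covariates as confounding. The first is gender; the other four are "use of release incision, the number of implants placed, whether or not bone regeneration (GBR) was applied and the distance from the implant apex", the last being measured to the mandibular canal. No planned or pre-operative version of the four surgical items is mentioned, and nothing says when each was decided.

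The Statistical analysis section uses these variables once by name: "Descriptive tables for the two primary variables were also tested by the five confounding variables". It also says "First, the homogeneity of two groups was verified", and the list of tests adds that "the chi-square and Fisher's exact tests were used as for groups homogeneity", without saying which variables were checked. The effect of group on pain or satisfaction is assessed by the Mann-Whitney test. No regression, adjusted comparison or stratified comparison of the two anesthesia methods is described.

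**The concern.** A confounder has to precede treatment or at least not result from it. Here the person who decides on the incision, the implants and the grafting knows the arm before starting. If the type of anesthesia changes how the surgeon operates, the four surgical features lie downstream of allocation. Three misreadings could then follow:

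- A difference between groups in, say, bone regeneration could be taken for a chance imbalance when it is an effect of the anesthesia.
- Similarity between groups on these features could be offered as evidence that randomization produced comparable groups, which it cannot show.
- An association of pain with one of these features could be presented as evidence of confounding. If someone then adjusted for the feature, part of the anesthesia effect could be removed or bias introduced.

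Of the five listed variables, only gender is certain to be fixed before the call.

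**Working it through.** **1. Order of events, from Study design.** The surgeon has a patient who needs implants, then phones and learns the arm, and operates thirty minutes later. The need for implant surgery therefore precedes the call. How much of the surgical plan also precedes it is not stated.

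| Variable | Wording | Fixed before the call? |
|---|---|---|
| Gender | patient attribute | Yes |
| Release incision | used | Not stated |
| Number of implants | placed | Not stated |
| Bone regeneration | applied | Not stated |
| Apex-to-canal distance | measured from the implant | Not stated |

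The wording allows the four features to be consequences of allocation. It does not show that they are.

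**2. Where the variables enter the analysis, from Statistical analysis.**

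- Primary group comparison: Mann-Whitney by group, with no covariate. None of the five enters.
- Spearman correlation between the two primary outcomes, and Friedman's test across the three pain times: none enters.
- Outcome breakdowns: all five enter. With 2 primary outcomes, 2 × 5 = 10 breakdowns, of which 2 × 4 = 8 use as-performed features. With the four NRS scores taken separately, 4 × 5 = 20, of which 4 × 4 = 16.
- Homogeneity check: variables not named. The five are the only covariates in the document, so at most 4 of 5 checks would use as-performed features. That is an inference.

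**3. What this does to the treatment estimate.** The stated null hypothesis is that the intervention is perceived equally under either anesthesia. That is a question about the total effect of allocation, including any part that runs through a changed operation. An unadjusted comparison of randomized groups estimates that total effect, whether or not the four features respond to the anesthesia. Bias from conditioning on a post-allocation feature needs a conditioning step, and none is planned.

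**4. The plan's own sample size, as a check that nothing here disturbs it.** Inputs: 24 per group, magnitude 0.8 read as a standardized difference, 5% level taken as two-sided (both readings are assumptions). With the Mann-Whitney efficiency under normality, 3/π = 0.955, the effective size is 24 × 0.955 = 22.9 per group. The noncentrality is 0.8 × √(22.9/2) = 2.71. The noncentral t distribution then gives power 75.4%, against the stated 75%; simulation of the Mann-Whitney test gives 75.7%. The figure reproduces and does not involve the five variables.

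**5. Power of the homogeneity tests.** Exact binomial enumeration, 24 per group, two-sided p < .05. The document gives no rates for these features, so the rates are assumed.

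| Assumed rates | Fisher | Chi-square (uncorrected) |
|---|---|---|
| 10% vs 30% | 31.4% | 43.1% |
| 20% vs 40% | 23.6% | 33.3% |
| 30% vs 50% | 21.4% | 31.0% |
| 40% vs 60% | 21.5% | 31.2% |

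A 20-point difference would go undetected between 100 − 43.1 = 56.9% and 100 − 21.4 = 78.6% of the time. These figures depend only on the group size and the two proportions. They would be identical for gender or for a planned value recorded before the call. They describe a limit of any balance test in 48 patients and do not measure the timing problem.

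**The case for a change.** The best argument for a change is that it costs little and the text supports it. The arm is known to the operator before the first incision, the four features are worded as performed, and they are tested against the primary outcomes under a name that implies they precede treatment. A reader could take a similar rate of bone regeneration in the two groups as proof of successful randomization, or could turn the breakdown tables into an adjusted analysis. Recording planned values before the call, naming the variables in the homogeneity table and relabelling the four items would prevent this.

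Part of that stands. Confounder is not a safe name for these items, and a claim of comparability at allocation should rest on variables fixed before the call.

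The rest does not lead to a change. The harm needs two steps that the document does not supply: that the features respond to the anesthesia, and that they are offered as evidence of balance. The common operating protocol or pre-call planning may have fixed some of them. The tables are already called descriptive, although they are also tested, and an association between pain and number of implants is a valid description whichever way causation runs. A ban on adjustment would forbid something not planned. The text is written as though patients were already enrolled, so pre-call form items might no longer be possible. The fallback of restricting the check to variables certainly fixed in advance would leave 1 of the 5, gender.

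**Conclusion.** The concern does not call for a change. The wording is loose, but followed as written the plan gives a sound unadjusted comparison of the randomized groups, and the effect of the label on that comparison is nil. The reach is limited to how 8 of 10 breakdowns (16 of 20 by separate score), and possibly up to 4 of 5 homogeneity checks, are described. Relabelling the variables, listing those in the homogeneity check or stating when each was fixed would alter no planned test of the anesthesia effect. A competent analyst would report the four features as characteristics of the operation and would not present them as baseline balance.

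This rests on two readings. First, the breakdowns relate the outcomes to each variable and are not treatment comparisons within strata; the list of tests supports this. Second, no adjusted analysis is intended, since none is described. If an adjusted or stratified treatment comparison using these features were added, their timing would become a real issue.

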## Statistical analysis

According to a previous calculation of the sample size, a minimum of 48 patients (24 per group) were determined to be necessary to reach a power of 75% with a Mann-Whitney test, a confidence level of 95% and a magnitude of 0.8 (strong) in pain level to be detected.

Data were tabulated to calculate descriptive statistics for all the variables of the investigation. Descriptive tables for the two primary variables were also tested by the five confounding variables. First, the homogeneity of two groups was verified. For the bivariate analysis, non-parametric tests were used:

- the chi-square and Fisher's exact tests were used as for groups homogeneity,
- the Mann-Whitney test to analyze the influence of the group on pain or satisfaction,
- the Spearman coefficient to measure the correlation between the two primary outcomes
- Friedman's test to check if the pain level was similar in incision, drilling and suturing.

For all tests, the significance level was set at 5% ( $p < .05$ ).

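### No listed analysis compares IANB with INF while holding any of the five recorded covariates fixed, and the homogeneity check is too weak at 24 per arm to show balance; the cost is precision and protection against chance imbalance, not validity

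*Combined protocol and SAP*

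**What the plan says.** Under Study design: "Five confounding variables were also recorded: gender, the use of release incision, the number of implants placed". The remaining two are bone regeneration (GBR) and the distance from implant apex to mandibular canal. Patients are randomised between IANB and INF, and the surgeon learns the arm by telephone thirty minutes before surgery.

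Under Statistical analysis, the five variables are used in two ways:

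- Against group: "the chi-square and Fisher's exact tests were used as for groups homogeneity".
- Against outcome: "Descriptive tables for the two primary variables were also tested by the five confounding variables".

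Group against outcome is a separate line: "the Mann-Whitney test to analyze the influence of the group on pain or satisfaction". The order and type of analysis are given as "First, the homogeneity of two groups was verified. For the bivariate analysis, non-parametric tests were used". The other two listed analyses are a Spearman correlation between the two primary outcomes and a Friedman test of pain across the three time points. All tests use the 5% level. The plan does not say what follows if homogeneity is rejected.

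**The concern.** Variables recorded because they may influence pain and satisfaction never enter the analysis that answers the trial's question. Relating a covariate to the outcome shows whether it is prognostic. It does not show what the IANB v INF difference would be with that covariate held fixed.

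The one step that addresses balance between the arms is a set of significance tests on 24 patients per arm. A non-significant result there says little: a split large enough to matter can pass, and the plan's wording then treats the groups as verified alike.

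Two things are at stake in a trial planned at only 75% power: precision that a prognostic baseline covariate could supply, and protection of the result actually obtained against a chance imbalance. A smaller consequence concerns the covariate-outcome tests. They appear to omit group, so they can pick up a group effect and attribute it to the covariate.

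**Working it through.** **Inputs from the documents.** 24 patients per arm; standardised difference 0.8; 5% level (two-sided assumed, as sidedness is not stated); Mann-Whitney test; 75% power. **Assumptions, because the documents give no figures:** covariate prevalence, covariate effect on NRS, and the share of NRS variance explained (R²). Each is shown over a range.

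**1. The plan's own figure.** "a minimum of 48 patients (24 per group) were determined to be necessary to reach a power of 75% with a Mann-Whitney test", for "a magnitude of 0.8 (strong) in pain level to be detected". Take two-sided t-test power with the sample size scaled by the normal-model efficiency of Mann-Whitney, 3/π. The effective n is 24 × 3/π = 22.9 per arm, which gives 75.4%. Direct simulation of the Mann-Whitney test (20,000 runs) gives 75.7%. The stated 75% is reproduced, and it belongs to the unadjusted test.

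**2. Power of the homogeneity check.** Exact enumeration of two binomials with n = 24:

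| True proportions | Fisher | Chi-square (uncorrected) |
|---|---|---|
| 50% v 25% | 34% | 45% |
| 40% v 60% | 21% | 31% |

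If all five variables were perfectly balanced in expectation and independent, at least one would still be flagged with probability up to 1 − 0.95⁵ = 22.6%.

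**3. Which splits pass.** Suppose a factor is present in 18 of 48 patients. The chance of an exact 12 v 6 split, in either direction, is 2 × C(18,12) × C(30,12) / C(48,24) = 2 × 0.0498 = 10.0%. It passes both tests (Fisher p = 0.135, chi-square p = 0.074). A 13 v 5 split is flagged by both (p = 0.036 and 0.017), and 13 v 5 or worse has probability 3.6%. So a split of 12 v 6 or worse occurs in about 13.5% of randomisations, but only the 10.0% at exactly 12 v 6 goes unflagged.

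**4. Type I error.** Simulation with NRS = round(2.5 + 2 × latent), truncated to 0–10, and no group effect. Averaged over all randomisations, unadjusted Mann-Whitney rejects in 4.6–5.0% for factor effects of 0.3–1.0 SD. Conditional on the 12 v 6 split:

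| Factor effect | Mann-Whitney |
|---|---|
| 0.3 SD | about 5.5% |
| 0.5 SD | about 6% |
| 0.8 SD | about 7.7% |
| 1.0 SD | about 9% |

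A regression of ranks on group and factor stays at about 5% conditional on the same split.

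**5. Power.** Group shift 0.8 SD, one binary baseline covariate:

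| Assumed R² | Unadjusted | Adjusted |
|---|---|---|
| 0 | about 74% | about 74% |
| 0.05 | 74–75% | about 76% |
| 0.1 | 74–75% | about 79% |
| 0.2 | 74–75% | about 83% |

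Adjusting for all five variables costs more. Allowing for the lost degrees of freedom and random covariate imbalance, power is about 70% at R² = 0 and breaks even with the unadjusted test at R² of about 0.1.

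**6. Covariate tests that omit group.** A covariate with no effect on the outcome, split 12 v 6, is called significant in about 8% when the group effect is 0.8 SD and about 11% when it is 1.2 SD.

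**7. Timing.** The arm is known before surgery starts. Of the five recorded variables, only gender is clearly fixed by then. Release incision, GBR, implants placed and apex-to-canal distance may be settled afterwards and could be affected by the anaesthetic method.

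**The case against.** The strongest reply is that this is a randomised trial, with the arm obtained from someone outside the study. *Confounding* is then a loose label for recorded covariates. The unadjusted Mann-Whitney test is valid, and it is the test on which the sample size was based. A reader might infer that the group comparison is biased, or that its false-positive rate exceeds 5%. The documents do not support that: step 4 shows that the overall error is held, and the excess appears only after an adverse split and with a sizeable factor effect. A reader might also infer that the plan offers the homogeneity check as its control of confounding. The plan never says so. It only gives no other step that addresses balance. This part of the reply stands.

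It is also true that no covariate-outcome association is reported, so the power gain is conditional on an assumed R². At R² near 0.02 there is essentially no gain. The larger conditional error rates need a factor effect of 0.8–1.0 SD, as large as the group effect that the plan calls strong. This also stands, and it limits the size of the point.

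A model using several of the recorded variables would be open to a further objection: most may be settled after allocation. The number of implants is recorded as placed, not as planned. The fix must therefore rest on gender. Surgeon is a reasonable further candidate for adjustment, but it is not among the five variables at issue here.

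What the reply does not remove is that a non-significant test at 24 per arm cannot verify balance, and that no listed analysis estimates the group effect with a covariate held fixed.

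**Conclusion.** The point holds as a matter of precision and of robustness to chance imbalance. The unadjusted comparison is valid overall. The homogeneity check is uninformative at this sample size (34% to 45% power against 50% v 25%), and a 12 v 6 split of a factor present in 18 of 48 patients, a one-in-ten event, goes through unflagged. The conditional consequence is small to moderate: about 6% to 9% rejection in place of 5%, for factor effects of 0.5 to 1.0 SD. The precision forgone ranges from nothing to about 8 points of power at R² from 0 to 0.2.

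Both ranges rest on assumed covariate effects, because the documents give none. They also rest on reading 0.8 as a standardised difference and on two-sided testing. The change is worth making because it costs almost nothing. It does not invalidate the planned test or the sample size.

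**What to change.** In Statistical analysis:

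1. For each NRS outcome, prespecify a group comparison adjusted for gender (rank ANCOVA or a proportional-odds model), to be applied whatever the balance table shows. Report the unadjusted Mann-Whitney test, which carries the 75% power, beside it.
2. Add the number of implants to that model only if the planned number is captured before the allocation call.
3. State when each of the five variables is determined. Keep release incision, GBR, implants placed and apex-to-canal distance to a sensitivity model.
4. Include group in any model used to read covariate effects.
5. Replace the homogeneity p-values, and the statement that homogeneity was verified, with a descriptive balance table by arm.

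The cost is SAP wording and a few lines of code, with a negligible loss of power if gender predicts nothing. Capturing the planned number of implants would need one extra item recorded at the call.

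### Surgeon is left out of the arm comparison; if the arms were balanced within surgeon, the planned Mann-Whitney p-value is conservative whenever surgeons differ

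*Combined protocol and SAP*

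**What the plan says.** The Study design section has 48 patients enrolled by "eight different surgeons in eight different private dental centers with similar settings and socio-professional characteristics, following the same operating protocol". Patients were randomized to two groups and "assigned in equal proportions to surgeons". An online list randomizer "was used as randomization method". The section does not say whether there was one list for the trial or one per surgeon, and it mentions no blocks or strata.

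The Statistical analysis section gives the arm comparison as "the Mann-Whitney test to analyze the influence of the group on pain or satisfaction". Surgeon is used in none of the listed tests and is not among the five recorded confounders. On sample size, "a minimum of 48 patients (24 per group) were determined to be necessary to reach a power of 75% with a Mann-Whitney test", for a magnitude of 0.8 at 95% confidence.

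On baseline balance the section says "First, the homogeneity of two groups was verified" and that "the chi-square and Fisher's exact tests were used as for groups homogeneity", without naming the variables tested.

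**The concern.** The phrase about equal proportions has two readings: 48/8 = 6 patients per surgeon, or 24/8 = 3 patients per arm within each surgeon. They lead to different analyses.

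Under the second reading, allocation was restricted within surgeon, so differences between surgeons cannot contribute to the difference between arms. The ordinary Mann-Whitney reference distribution assumes that all 48 patients could have been allocated freely. It therefore still counts surgeon differences as noise. Its p-value is too large, and power is given away in a trial sized for only 75%. Under the first reading with a single list, nothing is lost and the planned test is appropriate.

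**Working it through.** **Inputs.** From the documents: 24 per arm, magnitude 0.8, 5% level, eight surgeons. Assumed: 0.8 is in total-SD units; the test is two-sided; six patients per surgeon; surgeon accounts for a share ρ of pain variance between 0 and 30%. The documents give no value for ρ. The similar centers and the common operating protocol make the low end more plausible.

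**1. The plan's own figure.** Scale n by the Mann-Whitney efficiency 3/π: 24 × 0.955 = 22.92 per arm. The noncentrality is 0.8 × √(22.92/2) = 2.708 on 2 × 22.92 − 2 = 43.8 degrees of freedom. Power is 75.4%, so the stated 75% reproduces.

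**2. Why the test is conservative with arms 3:3 (approximation).** With total variance 1, the expected sample variance over 48 patients is (1 − ρ) + 42ρ/47, and the plain test uses this as its noise. Under allocation within surgeon the relevant variance is only 1 − ρ. The test statistic therefore has null SD √q, with q = (1 − ρ)/[(1 − ρ) + 42ρ/47], and the true size is 2[1 − Φ(1.96/√q)].

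- ρ = 10%: q = 0.900/0.989 = 0.910, √q = 0.954, size = 2[1 − Φ(2.055)] = 4.0%
- ρ = 20%: q = 0.800/0.979 = 0.817, √q = 0.904, size = 2[1 − Φ(2.168)] = 3.0%

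**3. Simulation, arms 3:3 within surgeon** (40,000 trials per cell, normal outcome, shift 0.8 total SD). Re-allocation means the same rank sum over all 48 patients, with its reference distribution taken from permuting the arms within surgeon.

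| Surgeon share | Size, planned | Size, re-allocation | Power, planned | Power, re-allocation |
|---|---|---|---|---|
| 0% | 4.9% | 5.0% | 75.1% | 75.1% |
| 5% | 4.3% | 4.9% | 76.1% | 77.2% |
| 10% | 3.9% | 4.9% | 75.9% | 78.6% |
| 20% | 3.2% | 5.0% | 77.6% | 83.2% |
| 30% | 2.4% | 5.0% | 79.0% | 87.3% |

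The sizes agree with the approximation in step 2. Separate simulations gave planned-test sizes of 3.9% at a share of 10% and 3.1 to 3.3% at 20%. With floor-heavy 0–10 scores (30% zeros assumed), power is 72.8% against 73.8% at 5%, and 74.5% against 79.7% at 20%. Unequal surgeon totals with balanced arms give 76.3% against 79.0% at 10%.

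**4. Simulation, one list of 24 + 24, not balanced within surgeon.**

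| Surgeon share | Power, planned | Power, surgeon-stratified |
|---|---|---|
| 0% | 74.4% | 67.4% |
| 10% | 75.4% | 72.1% |
| 20% | 75.6% | 76.5% |
| 30% | 76.3% | 81.8% |

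Here the planned test holds its size (4.6 to 4.9%). Stratifying costs 74.4 − 67.4 = 7.0 points at a share of 0 and roughly breaks even at 20%.

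**5. Which case applies can be checked.** Under one list, the chance that all eight surgeons end at 3:3 is C(6,3)⁸/C(48,24) = 20⁸/C(48,24) = 0.00079, or 0.08%. A given surgeon is 3:3 with probability 20 × C(42,21)/C(48,24) = 0.334, so on average 8 × (1 − 0.334) = 5.3 surgeons would not be. Arm counts by surgeon settle the question.

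**6. Side point on homogeneity.** At 24 per arm, power to detect 20% vs 40% is 24% (Fisher) or 33% (uncorrected chi-square); for 25% vs 50% it is 34% or 45%. An observed 5/24 vs 11/24 passes both tests (p = 0.125 and 0.066). A non-significant result does not verify balance.

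**The case against.** The strongest reply is that the plan contains no error. The planned test is valid under either reading. With a normal outcome and arms 3:3 it delivers 75.1 to 79.0% power, so the 75% target is met. The main recommendation rests on two facts the documents do not supply. One is balance within surgeon: the sentence is about patients, one outside person was phoned for allocations, and no per-surgeon list is described. The other is a material surgeon effect, against which the shared protocol and similar centers argue. At a share of 0 to 5% the gain is about 0 to 1 point. Applied to an unbalanced list, the remedy would do harm. The text is also in the past tense, so a change may come too late to be prespecified.

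All of this stands. It limits the weight of the point but does not remove it. The allocation sentence is ambiguous, the right reference distribution depends on how it is read, and a table of arm counts resolves it. The homogeneity wording and the covariate remarks are separate matters and add no weight to the point about surgeon.

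**Conclusion.** The point holds in its conditional form and is an optional improvement. If the arms were balanced within surgeon, the planned p-value is conservative when surgeons differ. Following the allocation gains 77.2 − 76.1 = 1.1 points of power at a 5% surgeon share, 78.6 − 75.9 = 2.7 at 10% and 83.2 − 77.6 = 5.6 at 20%. If surgeons do not differ, the cost is about 0.1 point, which disappears in the rounded figures. If the arms were not balanced within surgeon, the planned test should stay. Type I error is not inflated in either case, and the stated power is not overturned.

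The sizes depend on the assumed surgeon share, on six patients per surgeon and on 0.8 being in total-SD units. The low end of the range is the more likely.

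**What to change.** State whether the list was balanced within surgeon, and show arm counts by surgeon.

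- **If balanced:** for pain and satisfaction, keep the Mann-Whitney rank sum over all 48 patients, but take its p-value from re-allocating the arms within surgeon. Rank ANCOVA with surgeon as a fixed effect is nearly the same test. Report the ordinary Mann-Whitney p-value alongside. A van Elteren test is a poorer choice with strata of six: its power is about 70.6% when surgeons do not differ. Gender may be added, at a cost of about 0.8 point if it is unrelated to pain. Two further uninformative covariates would cost about 3 points (74.6% to 71.7%), so do not add more by default.
- **If not balanced:** keep the Mann-Whitney test as the main comparison and give a surgeon-adjusted result only as a sensitivity analysis.

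In either case, label the adjusted analysis post hoc if outcome data have already been seen. Present baseline balance descriptively and drop the claim that it was verified. Of the variables introduced by "Five confounding variables were also recorded: gender, the use of release incision, the number of implants placed", together with bone regeneration and apex-to-canal distance, all but gender appear to be intra-operative, though no recording time is given. Report these by arm, and do not adjust for them unless they were fixed before the allocation call.

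The cost is one or two sentences in the SAP and a look at the allocation list. Surgeon should already be known for every patient.

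### One null hypothesis and two primary outcomes, each tested at 5% with no rule joining them, and a pain variable that is never named

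*Combined protocol and SAP*

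**What the plan says.** The Study design section gives one null hypothesis, that "the intervention with either type of anesthesia is equally perceived by the patient". It then names two primary outcomes without ranking them: "The primary outcomes were pain perception by the patient during surgical procedure", together with satisfaction 12 hours after the operation. Data are collected on a "Numerical Rating Scale (NRS) four times, three for pain perception (after incision, after drilling, after suturing) and one for global satisfaction".

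The Statistical analysis section uses "the Mann-Whitney test to analyze the influence of the group on pain or satisfaction", and adds: "For all tests, the significance level was set at 5" percent. It gives no order of testing, no adjustment, and no statement that one or both outcomes must be significant.

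Two lines suggest a single pain score per patient. One reads "Descriptive tables for the two primary variables were also tested by the five confounding variables". The other plans one Spearman coefficient relating the two primary outcomes. Against that, the three readings are kept apart for Friedman's "test to check if the pain level was similar in incision, drilling and suturing". Neither section says which reading, or which summary of the three, is compared between groups.

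The sample-size paragraph refers to one Mann-Whitney test and an effect of 0.8 in pain level, with 24 patients per group and 75% power. It gives no effect for satisfaction.

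The text is in the past tense (patients "were enrolled in this prospective study, by eight different surgeons"), so it does not show whether the groups had already been compared when it was written.

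**The concern.** A null hypothesis that the two anesthesias are perceived alike is contradicted by a difference on either outcome. Read literally, the plan therefore gives two chances at 5% each to reject one hypothesis, and the error rate for that hypothesis exceeds 5%. If the sponsor instead means that both outcomes must differ, the error rate is safe, but the chance of success falls below the 75% in the sample-size paragraph. The plan does not say which is meant, so the level and power for its single null are undefined.

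The unnamed pain variable adds a second gap. With three readings and no stated choice, the reading or summary to be claimed could be selected after the results are seen. A reader could not tell a prespecified result from the most favourable of several.

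**Working it through.** **Inputs from the Statistical analysis section:** 24 per group, effect 0.8, Mann-Whitney, 5% level, power 75%.

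**Assumptions, not in the documents:** two-sided testing; 0.8 as a standardized difference; normal scores rounded to a 0–10 scale (mean 5, SD 2) in the simulations; an effect of 0.8 on satisfaction where stated; correlation between outcomes from 0 to 0.9. Pain and satisfaction would probably correlate negatively. With two-sided tests and effects in matching directions, reversing one scale changes nothing.

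**1. The plan's own figure.** Use t-test power with the sample size multiplied by the Mann-Whitney relative efficiency for normal data, 3/π = 0.955.
- Effective size: 24 × 0.955 = 22.9 per group.
- Noncentrality: 0.8 × √(22.9/2) = 2.71.
- Two-sided power at 5%: 75.4%. With 23 per group it is 73.6%, so 24 is the smallest size that reaches 75%.
- A one-sided test would give 84.6%, so the stated figure fits one two-sided, unadjusted test.

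**2. Either outcome rejects the null.**
- False-positive rate if independent: 1 − 0.95² = 9.75%.
- Simulated: 9.4% at correlation 0, 8.9% at 0.5, 7.8% at 0.8 and 7.3% at 0.9. Repeat runs span about 7 to 9.5%.
- Power if both effects are 0.8 and independent: 1 − 0.25² = 94%. At correlation 0.9, 2 × 75% − 68% = 82%.

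**3. Both outcomes must be significant.**
- No inflation.
- Power if both effects are 0.8 and independent: 0.75² = 56%. Simulated: 55.5% at correlation 0, 61.2% at 0.5 and 67.8% at 0.9.
- If scores pile up at the ends of the scale (assumed underlying means 0.5 for pain and 9.5 for satisfaction), single-test power is about 71–72% and joint power 51–64%. The either-outcome error hardly moves (7.6–9.5%).

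**4. Holm** (smaller p-value against 2.5%, then the larger against 5%). Simulated power of one test is about 64% at 2.5% and 75% at 5%.
- Both effects 0.8, independent: 64% + (75% − 64%) × 64% = 71%. Simulated: 70.5% at correlation 0 to 68.4% at 0.9.
- Only that outcome differs: about 64%.

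**5. Fixed order, pain first.**
- Pain keeps its 75%.
- If both effects are 0.8, satisfaction is claimed as often as both are significant in step 3.
- If only satisfaction differs and the outcomes are independent, it is claimed in 5% × 75% = 3.75% of trials. Simulated: 3.7% at correlation 0 to 2.6% at 0.9.

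**The case against.** The strongest reply is that two separate claims at 5% each are legitimate, and that each test does have a stated level. That is true, and it would settle the matter if the plan stated two hypotheses. It states one, so something must say what rejects it.

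A second reply is that the pain score is not really ambiguous: the Spearman line and the reference to two primary variables presuppose one score per patient, and Friedman's test compares phases, not groups. This largely stands. It makes two primary tests the better-supported reading, but it does not say which of the three readings, or which summary, that score is.

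A reader might infer that four group tests are planned and put the error far higher. Simulation gives 9.8% with all correlations 0.9 and 15.5% with all 0.5; the formula gives 1 − 0.95⁴ = 18.5% if independent, which is implausible within one operation. The documents give little support for separate group tests of all three phases, so this is a side case.

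A reader might also infer that neither the error rate nor the power of the trial is known. That goes too far. The pain test, once its variable is named, keeps its 5% level and its 75% power, and the either-outcome rule raises power as well as error. Nor does it follow that satisfaction is underpowered: the same sample gives about 75% for an effect of 0.8 there too. What is missing is any effect size for it.

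**Conclusion.** The point holds as a cheap improvement to the wording. For the single null as stated, the plan fixes neither the level nor the power:

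- Either-outcome rule: about 7–9.5% false positives and about 82–94% power.
- Both-required rule: no inflation and about 55–68% power, somewhat lower if scores cluster at the ends of the scale.

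The power figures assume an effect of 0.8 on both outcomes, and all ranges rest on assumed correlations. The sample-size calculation is correct for the one test it describes.

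The primary pain variable is undefined. That leaves room for a choice after the results are seen; the documents do not show that such a choice was made.

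**What to change.** Before any comparison by group:

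1. Name one primary pain variable, either a prespecified reading or a prespecified summary of the three. Report the other phase comparisons as secondary.
2. State one rule for the two primary outcomes. Holm keeps their equal status. A fixed order with pain first is suitable if the sponsor ranks pain higher. If two separate claims are intended, replace the single null with two hypotheses and do not claim rejection of an overall null.
3. State that the 75% power applies to the pain test alone and that no effect size was set for satisfaction.

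**Cost.** No extra patients. Holm lowers the power for each outcome from 75% to about 68–71% if both effects are 0.8, or to about 64% if only that one differs. The fixed order leaves pain at 75%, but satisfaction is then claimed in only about 3–4% of trials if it alone differs. The choice of pain variable also matters. Simulated power for a mean of the three readings is 81–90% if all phases differ by 0.8, 47–58% if two do and 16–19% if one does (pain correlations 0.8 to 0.5). A single reading has about 75% only if it is one where the effect lies.

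Because the text is in the past tense, the sponsor should confirm whether the groups have been compared. If they have, these choices cannot restore confirmatory error control. In that case report satisfaction and all three pain comparisons, label the choice of pain variable and rule as post hoc, and call the result exploratory.
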